9.6.1 Adverse Events

Adverse events will be coded to System Organ Class and preferred term using the Medical Dictionary for Regulatory Activities (MedDRA) version adopted at the start of the double-blind study in which the subject previously participated (Version 15.0 or later).

Adverse events will be regarded as treatment-emergent (TEAE) if they start on or after the first dose of study drug administration in the open-label study or if they were present prior to the first date of study drug administration and increased in severity or relationship to study drug while on study treatment. Those that resolved prior to the first dose or were ongoing at the same intensity and relationship will be regarded as pre-treatment AEs and not summarized.

Tabular summaries are described below, with the number and percentage of subjects reporting each type of event presented. If a subject reports the same preferred term more than once, it is counted only once within that category. Further, for a given tabulation, the preferred term will only be counted once in its worst severity, greatest relationship to treatment, and worst action taken.

Pre-study AEs, those present at the time of the first dose of study drug administration, will be presented separately.

An overall summary table of TEAEs will be produced showing the number and percent of subjects with the following: TEAE, severe intensity TEAE, TEAE related to study drug, AESIs, serious TEAE, TEAE with outcome of death, and TEAE leading to interruption, dose reduction, or discontinuation from the study. In addition, the summary table will include the number of TEAEs, severe TEAEs, TEAEs related to study drug, and serious TEAEs.

Separate summaries of incidences (number and percentage of subjects) of all individual TEAEs and the subsets of drug-related TEAEs, TEAEs that are severe in intensity, serious TEAEs, and TEAEs leading to change in dose will be provided.

The subset of TEAEs that have an onset more than 7 days after the last dose of study drug will be considered post-treatment. An overall summary table of the number and percent of subjects with post-treatment AEs will be prepared.

All AEs will be presented in a data listing. In addition, listings also will be provided for SAEs, AEs leading to death, AEs leading to discontinuation of study drug, AEs leading to dose reduction and/or interruption, and any other AEs that are of special interest (to be defined prior to database lock).

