## **7. SAFETY ANALYSES**

### **7.1 Adverse Events**

There are two CRFs contributing adverse event data.

- **Prior Study – Adverse Events CRF:** All adverse events as recorded during prior studies 005, 007 and 015 will be automatically uploaded to the Prior Study – Adverse Events CRF and adverse events recorded during the 008 study will be recopied from the 008 records by the site to the Prior Study – Adverse Events CRF. The only field that can be modified by the site is the OLEX end date as applicable. Additionally there is a comment field where text can be entered by site.
- **Adverse Event CRF:** New adverse events or changes to an existing adverse event will be recorded on the Adverse Event CRF.

Adverse events will be coded to SOC and PT using MedDRA (version 16.0). The coding process is described in the Data Management Plan.

AEs are grouped as follows and source(s) of data identified:

1. **Prior AEs:** AEs that were ongoing at the end of the prior study but that resolved before Day 1 of dosing in 020 or that started and resolved during the gap between studies. The source would be both the Prior Study – Adverse Events CRF and the (020) Adverse Event CRF.
2. **Pre-existing AEs:** AEs that were ongoing on Day 1 of dosing in 020 - source is the Prior Study – Adverse Events CRF. The source would be both the Prior Study – Adverse Events CRF and the (020) Adverse Event CRF.

3. Study-emergent AEs: AEs that started on or after Day 1 of dosing in 020, excluding post-treatment AEs (defined in #5 below). The source would be the (020) Adverse Event CRF.
4. All AEs: Whether pre-existing or study-emergent (merge of AEs that were ongoing on Day 1 of dosing) excluding post-treatment AEs. Sources are the Prior Study – Adverse Events CRF and the (020) Adverse Event CRF (note, this is a merge of #2 and 3 above *only*).
5. Post-treatment AEs: The study-emergent AEs (3# above) that have an onset more than 14 days after the last dose of study drug or that worsen in intensity or treatment attribution following discontinuation more than 14 days after the last dose of study drug.

The tabular summaries will be provided for AEs, with the number and percentage of subjects reporting each type of event. If a subject reports the same preferred term more than once, it is counted only once within that category. Further, for a given tabulation, the preferred term will only be counted once at its worst severity and strongest relationship to treatment.

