## 7.2 Clinical Laboratory Evaluation

Central laboratory data are transferred electronically by Covance. The Data Transfer Specification document provides a detailed description of the content and format of the laboratory datasets. Both conventional and SI units are provided and will be summarized in separate tables and listings. The eGFR values will be calculated and included in the tables and listings for clinical chemistry parameters.

Results from local laboratories are entered into the CRF by the site; these will not be included in summary tabulations but will be included in the data listings together with the corresponding normal ranges. Values for local laboratory parameters will be converted to the corresponding alternative units, either conventional or SI, depending on how reported.

For the summary tabulations of laboratory results, Baseline is defined as the last non-missing value prior to first dose of study drug in 020. Laboratory tests obtained on the date of the first dose will be assigned to pre-treatment. For each analyte, Baseline values will be restricted to those subjects in the safety population for whom there is at least one post-Baseline value (either overall or for the corresponding target visit). Any lab result 14 or more days after the last dose will be considered post-treatment.

Visit windows are used when results are presented by target visit (see [Appendix A](#)). For each analyte, if a subject has multiple values within a visit window, the “worst” value as defined in [Appendix D](#) will be used for that visit window summary.

Results of all continuous laboratory parameters will be summarized using descriptive statistics at baseline and at each post-baseline target visit; the last available on-treatment value and post-treatment results will also be summarized. The baseline data may come from the prior study, if not repeated in 020. For each subsequent target visit, changes from baseline will also be summarized by the number and percentage of subjects and the mean, median, SD, minimum, and maximum values for continuous laboratory parameters. These will also be prepared for subjects categorized by diagnosis and AChEI/Memantine use.

Box and whisker plots will be presented for selected parameters including hemoglobin, reticulocytes (%), neutrophils, and liver function tests. Other parameters may be identified during data review.

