## **9. CHANGES TO PROTOCOL-SPECIFIED ANALYSES**

Any changes will be documented in the Clinical Study Report in Section 9.8.

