**Table 14.3.2.15.1**  
**Post-Treatment Adverse Events by System Organ Class and Preferred Term**  
**Safety Population**

System Organ Class / Preferred Term	AD (N= )		bvFTD (N= )		All Subjects (N= )	
	Subjects 	Events	Subjects 	Events	Subjects 	Events
Subjects Reporting at Least One Adverse Event	n (%)	n	n (%)	n	n (%)	n
System Organ Class 1	n (%)	n	n (%)	n	n (%)	n
Preferred Term 1	n (%)	n	n (%)	n	n (%)	n
Preferred Term 2	n (%)	n	n (%)	n	n (%)	n
.						
.						
System Organ Class 2	n (%)	n	n (%)	n	n (%)	n
Preferred Term 1	n (%)	n	n (%)	n	n (%)	n
Preferred Term 2	n (%)	n	n (%)	n	n (%)	n

Note: Post-treatment adverse events are defined as TEAEs that have an onset more than 14 days after the last dose of study drug.

 At each level of summation (overall, system organ class, preferred term), subjects reporting more than one adverse event are counted only once.

path\t\_program.sas date time

*Programming Note: Repeat table for Table 14.3.2.15.2 Post-Treatment Adverse Events by System Organ Class and Preferred Term – Non-AChEI/Memantine Users (Safety Population)*

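### Post-treatment AEs start more than 7 days after last dose in the protocol but more than 14 days in the SAP, which also removes them from the study-emergent tables; neither change is declared

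*Protocol*

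**What the plan says.** **Protocol 9.6.1.** An AE is treatment-emergent if it begins on or after the first open-label dose. No end date is set for this status. The section then says: "The subset of TEAEs that have an onset more than 7 days after the last dose of study drug will be considered post-treatment". These events get their own overall summary table. Nothing in the section takes them out of the TEAE tables.

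**SAP 7.1.** AEs are sorted into five groups.
- Group 3 (study-emergent) is defined as "AEs that started on or after Day 1 of dosing in 020, excluding post-treatment AEs".
- Group 4 combines pre-existing and study-emergent AEs, with the same exclusion.
- Group 5 (post-treatment) takes events "that have an onset more than 14 days after the last dose of study drug". It also takes late worsening, which is not part of this point.

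**SAP Appendix G, note to Table 14.3.2.15.1.** "Post-treatment adverse events are defined as TEAEs that have an onset more than 14 days after the last dose of study drug".

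**SAP 7.2.** For laboratory data: "Any lab result 14 or more days after the last dose will be considered post-treatment". The follow-up window in SAP Appendix A also opens at 14 days.

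**Declaration of changes.** SAP Section 1 gives protocol Version 3.0 as its basis, so the two texts should agree. SAP Section 9, the place for changes to protocol-specified analyses, contains one sentence: "Any changes will be documented in the Clinical Study Report in Section 9.8".

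**The concern.** The documents differ in two ways. The cut-off day moves from 7 to 14. The relation between the two classes also changes: in the protocol, post-treatment AEs are a labelled part of the TEAEs, while in the SAP they form a separate class that is taken out of the study-emergent tables. The SAP is not consistent on the second matter. Group 5 is described as drawn from the study-emergent events, and the table note still calls them TEAEs, yet group 3 excludes them.

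The class decides which tables an event reaches. Groups 2 to 4 feed the overall, severity, relationship, serious, severe, dose-change and AESI summaries. Group 5 is tabulated only by system organ class and preferred term. Long-term safety and tolerability is a primary objective, and a 4-week follow-up visit is scheduled for everyone who stops LMTM. A reader of the report should be able to tell which off-drug events each table holds, and whether that matches the protocol.

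**Working it through.** **Inputs.** Protocol AE cut-off: more than 7 days (9.6.1). SAP AE cut-off: more than 14 days (7.1 group 5; Table 14.3.2.15.1 note). Follow-up visit: 28 ± 14 days after last dose (protocol Appendix A), so Days 14 to 42. Laboratory cut-off: 14 or more days (SAP 7.2 and Appendix A). Days are whole days after the last dose. The plan gives no figure of its own to reproduce.

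**Step 1: classify new onsets by day.**

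| Onset, days after last dose | Protocol | SAP |
|---|---|---|
| 1–7 | TEAE | Study-emergent |
| 8–14 | TEAE, and in the post-treatment summary | Study-emergent only |
| 15 or later | TEAE, and in the post-treatment summary | Post-treatment table only |

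The post-treatment label differs on exactly seven days, 8 to 14. Membership of the main tables differs from Day 15 on.

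**Step 2: length of the post-treatment period** for follow-up on day F. Protocol: F − 7. SAP: F − 14. Share reclassified: 7 / (F − 7).

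| F | Protocol | SAP | Share of days |
|---|---|---|---|
| 14 | 14 − 7 = 7 | 14 − 14 = 0 | 7/7 = 100% |
| 28 | 28 − 7 = 21 | 28 − 14 = 14 | 7/21 = 33% |
| 42 | 42 − 7 = 35 | 42 − 14 = 28 | 7/35 = 20% |

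**Step 3: off-drug days whose onsets enter the main tables**, with F = 28.
- Protocol TEAE tables: all 28 days.
- SAP study-emergent tables: Days 1–14, so 14 days; 28 − 14 = 14 are left out.
- SAP with 7 put in place of 14 but the exclusion kept: Days 1–7, so 7 days; 28 − 7 = 21 are left out.

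Changing the number alone would therefore take the main tables further from the protocol.

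**Step 4: Day 14 within the SAP.** For AEs, 14 > 14 is false, so an onset that day is study-emergent. For laboratory values, 14 ≥ 14 is true, so blood drawn that day is post-treatment. Day 14 is also the earliest in-window follow-up day, so both can arise at one visit.

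**The case against.** The strongest case against has four parts.

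1. **Changes are deferred to the study report.** Both documents say so (protocol Section 9; SAP Section 9), so the SAP's silence breaks neither. This is fair as to procedure. It does not remove the conflict between two stated rules, and the SAP already contains the change, so it can be declared now with a reason.
2. **Fourteen days may be the better choice.** The early termination visit may fall up to 14 days from last dose and follow-up may begin at Day 14. That could justify the SAP rule, but the SAP does not say it.
3. **Nothing is lost.** All AEs are listed with study day, last-dose dates are listed, SAEs and AESIs have listings that include post-treatment events, and Day 8–14 events reach more tables under the SAP than under a bare post-treatment label. This stands: the events stay visible and can be recounted. But the post-treatment flag in the AE listings follows the 14-day rule, so no planned output shows the protocol's count.
4. **The laboratory rule is not a protocol conflict.** Correct. Protocol 9.6.2 sets no post-treatment laboratory boundary, and SAP 7.2 agrees with SAP Appendix A. Only the Day 14 mismatch with the AE rule remains.

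**Conclusion.** The contradiction is certain on the text and undeclared. AEs with onset on Days 8–14 are absent from the post-treatment summary as the protocol defines it. AEs after Day 14 are absent from the SAP's study-emergent tables although they are TEAEs in the protocol. At a Day 28 follow-up these gaps cover 7 of 21 post-treatment days and 14 of 28 off-drug days.

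The effect is limited. Counts change only for subjects with an AE starting in those periods, and the safety analysis is descriptive, so no test or decision rule depends on it. The point is worth correcting because the repair is cheap and alters reported safety counts.

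Two stronger readings are tempting and are not supported. A reader might infer that the SAP credits an extra week of off-drug time to treatment and so inflates the main tables relative to the protocol. The protocol's TEAEs have no upper time limit, so the SAP's main tables hold fewer off-drug onsets, not more. A reader might also infer that a third of post-treatment events are lost. The 33% is a share of calendar days; the documents give no onset rates.

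The conclusion assumes that the protocol's TEAE tables keep post-treatment events. The protocol does not say so outright, but it follows from calling them a subset of TEAEs and stating no exclusion. The day counts run to the follow-up visit; later reports remain possible.

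**What to change.** Choose one of two routes.

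- **Follow the protocol.** Put more than 7 days in SAP 7.1 group 5 and in the Table 14.3.2.15.1 note, and delete the exclusion of group 5 from groups 3 and 4. Post-treatment AEs then become a flagged subset of study-emergent AEs. Both edits are needed together, as Step 3 shows.
- **Keep the SAP.** Retain 14 days and the exclusion, and list both in SAP Section 9 as changes from protocol 9.6.1, each with a reason.

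On either route, add a row to Table 14.3.2.15.1 for AEs with onset on Days 8–14 after last dose, so that both counts can be read.

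Separately, settle Day 14. If the 14-day AE rule stays, use the same inequality in 7.1, the table note, 7.2 and Appendix A. If the 7-day AE rule is adopted, Day 14 is post-treatment for both kinds of data; state that laboratory results keep their own boundary. The 7-day rule need not be applied to laboratory data.

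The cost is a few lines of SAP text, one table note and one table row. No new data are needed.

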9.6.2 Laboratory Tests

Descriptive statistics will be based on central laboratory results as described below. Laboratory results that are obtained from laboratories other than the central laboratory will not be included in tabular summaries. They will, however, be listed separately. Normal ranges will be provided by the central laboratory and each local laboratory used for testing parameters other than Heinz bodies.

Categorical laboratory parameters will be summarized for each target visit using counts and percent of subjects in each result category. Continuous laboratory parameters will be summarized for each target visit using descriptive statistics for both the original values and the change from Baseline. For each analyte, Baseline values will be restricted to those subjects in the Safety Population for whom there is at least one post-Baseline value.

Selected parameters for which normal ranges differ may additionally be summarized by gender, age, and country (or region).

Box and whisker plots will be presented for selected parameters including hemoglobin, reticulocytes, neutrophils, and liver function tests.

Shift tables will be provided cross tabulating the number of subjects who are low, normal, or high at Baseline (with respect to the normal range) against results at each target week.

Potentially clinically significant ranges will be defined in the SAP for selected parameters, and the number and percent of subjects meeting these criteria summarized. Tabular summaries will be based on those subjects who meet criteria at Baseline and those in whom the values represent a treatment-emergent worsening.

Listings of laboratory parameters will be presented. Listings will flag results above and below the normal range as well as those that meet criteria for being potentially clinically significant (whether or not a treatment-emergent worsening). Separate listings for each hematology and chemistry parameter will show results that meet criteria for being potentially clinically significant. In addition, for subjects who have one or more result that meets criteria, all laboratory results will be displayed.

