7.1.3.1 Hemolytic Anemia

The subject should be evaluated at each visit for possible clinical symptoms associated with hemolytic anemia, in conjunction with review of hematology results. Should hemolytic anemia be suspected, follow-up testing should be performed as described in Section 7.3.2. The medical monitor should be contacted to discuss whether or not resumption of dosing is indicated or for any other questions.

The signs and symptoms of anemia include:

- Cyanosis, headache, anxiety, exercise intolerance, fatigue, confusion, dizziness, tachypnea, palpitation, dysrhythmia, seizures, and coma

Signs of possible hemolytic anemia include:

- Decrease by 20% from Baseline in RBC count and/or hemoglobin
- Abnormal RBCs in peripheral blood smear
- Elevation of reticulocyte count to above laboratory normal range
- Increase in LDH or indirect bilirubin, or low haptoglobin

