7.3.1 Serum Chemistry

The blood volume for each chemistry panel will be approximately 3.5 mL. Blood samples collected for serum chemistry panels are to be destroyed approximately 1 week after testing has been completed. The chemistry panel will include the following analytes:

Sodium	Gamma-glutamyl transpeptidase (GGT)
Potassium	Alanine transaminase (ALT)
Calcium	Aspartate transaminase (AST)
Albumin	Glucose (random, not fasted)
Total protein	Creatinine ²
Urea nitrogen, urea ¹	Phosphorus
Total and direct (conjugated) bilirubin (indirect bilirubin calculated as the difference)	Uric acid
Alkaline phosphatase	Chloride
Lactate dehydrogenase (LDH)	Creatine kinase (CK)

¹ The analytical method measures urea in serum. In the Covance CLS database, the test is named either Urea Nitrogen or Urea, depending on whether the results are expressed in conventional or SI units, respectively. Urea Nitrogen is reported in mg/dL while Urea is reported in mmol/L per SI unit convention.

² Creatinine clearance is to be estimated by the central laboratory using the Cockcroft-Gault equation.

7.3.2 *Hematology*

The blood volume for each hematology panel will be approximately 2.0 mL. Blood samples collected for hematology panels are to be destroyed approximately 3 days after testing has been completed. The hematology panel will include the following analytes:

Hematocrit	White blood cells (WBC)
Hemoglobin	and absolute and percent differential
Mean corpuscular hemoglobin (MCH)	(neutrophils, lymphocytes, monocytes, eosinophils, basophils); any abnormal cells
Mean corpuscular hemoglobin concentration (MCHC)	will be noted
Red blood cells (RBC) and any immature forms	Platelet count
RBC morphology	Mean cell volume (MCV)
Reticulocyte count and percent	

If the investigator is concerned on the basis of significant hematological abnormalities that Heinz bodies may be present, a blood sample may be sent to the local laboratory for assessment and screening of Heinz bodies. The percent of erythrocytes with Heinz bodies should be reported based on a suitably prepared slide; blood samples should be as fresh as possible at the time of slide preparation. If Heinz bodies are present, study medication must be stopped (see Section 6.2.3.1) and another blood sample should be obtained within 1 week. Hematological indices should continue to be monitored until this resolves.

7.3.3 *Other Laboratory Tests*

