**Appendix B: Criteria for Determining Potentially Clinically Significant Values in Laboratory Test Results**

Test	Criteria	
	System International Units	Conventional Units
Hemoglobin	Female: $\leq 95$ g/L; Male: $\leq 115$ g/L Decrease of $\geq 20\%$	Female: $\leq 9.5$ g/dL; Male: $\leq 11.5$ g/dL
Hematocrit	Female: $\leq 0.32$ ; Male: $\leq 0.37$	Female: $\leq 32\%$ ; Male: $\leq 37\%$
WBC count	$\leq 2.8 \times 10^9/L$ $\geq 16 \times 10^9/L$	$\leq 2800/\mu L$ or $\geq 16000/\mu L$
Neutrophils	$\leq 1.0 \times 10^9/L$	$\leq 1000/\mu L$
Eosinophils	$\geq 0.7 \times 10^9/L$	$\geq 700/\mu L$
Platelet count	$\leq 75 \times 10^9/L$ $\geq 700 \times 10^9/L$	$\leq 75 \times 10^3/\mu L$ $\geq 700 \times 10^3/\mu L$
Sodium	$<130$ mmol/L $>150$ mmol/L	$<130$ mEq/L $>150$ mEq/L
Potassium	$< 3.0$ mmol/L $> 5.5$ mmol/L	$< 3.0$ mEq/L $> 5.5$ mEq/L
Calcium	$< 1.75$ mmol/L $> 3.00$ mmol/L	$< 7.00$ mg/dL $> 12.00$ mg/dL
Glucose, fasting/nonfasting/unknown	$< 2.775$ mmol/L $>13.875$ mmol/L	$< 50$ mg/dL $> 250$ mg/dL
Uric acid	Female: $>475.8$ $\mu\text{mol/L}$ ; Male: $>594.8$ $\mu\text{mol/L}$	Female: $> 8$ mg/dL; Male: $>10$ mg/dL
Albumin	$<25$ g/L	$<2.5$ g/dL
Total bilirubin	$\geq 34.2$ $\mu\text{mol/L}$	$\geq 2$ mg/dL
ALT	$\geq 3 \times \text{ULN}$	$\geq 3 \times \text{ULN}$
AST	$\geq 3 \times \text{ULN}$	$\geq 3 \times \text{ULN}$
Alkaline phosphatase	$\geq 3 \times \text{ULN}$	$\geq 3 \times \text{ULN}$
Urea (nitrogen)	$> 17.85$ mmol/L	$> 50$ mg/dL
Creatinine	$\geq 177$ $\mu\text{mol/L}$	$\geq 2$ mg/dL
CK	$\geq 3 \times \text{ULN}$	$\geq 3 \times \text{ULN}$
GGT	$\geq 3 \times \text{ULN}$	$\geq 3 \times \text{ULN}$
LDH	$\geq 3 \times \text{ULN}$	$\geq 3 \times \text{ULN}$
Phosphorus	$< 0.646$ mmol/L $> 1.777$ mmol/L	Low: $<2.0$ mg/dL High: $>5.5$ mg/dL

ULN = Upper Limit of Normal

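### The SAP omits the protocol's laboratory shift tables and categorical counts, so several protocol-named signs of haemolysis are counted in no laboratory table

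*Protocol*

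**What the plan says.** Protocol 9.6.2 makes two firm commitments for central-laboratory data. The first is the shift table: "Shift tables will be provided cross tabulating the number of subjects who are low, normal, or high at Baseline", crossed with results at each target week. The second is for non-numeric results: "Categorical laboratory parameters will be summarized for each target visit using counts and percent of subjects in each result category". Neither is optional. The same section uses permissive wording only for the extra summaries by gender, age and country.

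Protocol 7.1.3.1 lists laboratory signs of possible haemolytic anaemia. Besides a 20% fall in RBC count or haemoglobin, they are "Abnormal RBCs in peripheral blood smear", "Elevation of reticulocyte count to above laboratory normal range" and "Increase in LDH or indirect bilirubin, or low haptoglobin". The central haematology panel in Protocol 7.3.2 includes "RBC morphology" and reticulocytes as count and percent.

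SAP 7.2 states: "Results of all continuous laboratory parameters will be summarized using descriptive statistics at baseline and at each post-baseline target visit". It adds change from baseline, box plots for selected parameters, the incidence of potentially clinically significant (PCS) values, and listings. The PCS limits are in Appendix B, headed "Criteria for Determining Potentially Clinically Significant Values in Laboratory Test Results". SAP 7.2 mentions no shift table and no summary of categorical laboratory results. SAP section 9 says only that any changes will be documented in the study report.

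**The concern.** Long-term safety is a primary objective. Haemolytic anaemia is one of two adverse events of special interest (AESIs), and Protocol 4.7.8 refers to a risk of anaemia with MT. The protocol defines the reticulocyte sign against the normal range, so the natural summary is how many subjects moved from normal to high, which is what a shift table gives. A mean, a median or a box plot cannot give that number, and a listing gives no rate. If the only laboratory count is the PCS table, a low count there could be read as little haemolysis when several of the protocol's own signs were never eligible to be counted.

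**Working it through.** No sample size or error rate is involved. The check sets the protocol's commitments beside the SAP's outputs.

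**Step 1: laboratory tables in Appendix F.** There are 4 haematology value/change tables (14.3.3.1.x), 4 serum chemistry value/change tables (14.3.3.2.x) and 2 PCS incidence tables (14.3.3.3.1 and 14.3.3.3.2): 4 + 4 + 2 = 10. The value/change shells show n, mean (SD), median, minimum and maximum. Shift tables: 0 of 10. Category tables: 0 of 10. The only baseline-by-visit cross-tabulation in the SAP is for ECG interpretation (Table 14.3.4.5.2).

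**Step 2: which haemolysis signs can be counted.** Only the two PCS tables count subjects with abnormal laboratory results, and they use the 22 tests in Appendix B.

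| Sign (Protocol 7.1.3.1) | Counted in a laboratory table? | Otherwise shown |
|---|---|---|
| Haemoglobin fall of 20% | Yes (fall of at least 20%, plus absolute limits) | Statistics, box plots, listing |
| RBC count fall of 20% | No criterion | Statistics, listing |
| Abnormal RBCs on smear | No criterion | No table or listing layout |
| Reticulocytes above range | No criterion | Statistics, box plots, listing |
| LDH increase | Only at 3 x ULN or more | Statistics, listing |
| Indirect bilirubin increase | Only through total bilirubin of 2 mg/dL (34.2 µmol/L) or more | Statistics, listing |
| Low haptoglobin | No, but it is not in the central panel | Local-laboratory listing |

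Haptoglobin is not part of this point, because Protocol 9.6.2 itself keeps local-laboratory results out of the tables.

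**Step 3: how far the total-bilirubin criterion reaches.** Protocol 7.3.1 calculates indirect bilirubin as total minus direct, so indirect cannot exceed total. An indirect value of 2 mg/dL or more therefore forces total to 2 mg/dL or more and meets the criterion. A smaller rise in indirect bilirubin is caught only if direct bilirubin brings the total up to 2 mg/dL.

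**Step 4: whether Listing 16.2.8.5.3 closes the gap.** Its title refers to haemoglobin, haematocrit and reticulocytosis, but it is a listing. Its programming note triggers it when RBC or haemoglobin meets a PCS criterion. Appendix B has no criterion for RBC or reticulocytes, so an isolated reticulocytosis would not trigger it.

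**Step 5: RBC morphology.** The value/change shells hold only numeric statistics, and the layout of central haematology Listing 16.2.8.2.1 has no column for it.

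**The case against.** The SAP is not silent on haemolysis, and four points stand against a broad claim.

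- Appendix B counts low haemoglobin, a haemoglobin fall of at least 20%, low haematocrit, total bilirubin of at least 2 mg/dL and LDH of at least 3 x ULN. What is missing is mainly sensitivity to moderate changes. A reader might infer that almost none of the laboratory picture is counted; the documents do not support that.
- Clinically significant laboratory abnormalities are to be recorded as adverse events, and SAP 7.1 counts AESIs by subject and event. It would therefore be wrong to say these signs are counted in no table. The tables in SAP 7.1 depend on investigator reporting, however, and do not replace a count from the laboratory data.
- SAP section 4 has general rules that categorical variables are summarised by counts and percentages and that central-laboratory data are listed by subject. A reader might infer from the shells that RBC morphology will never reach the report, or that the SAP summarises continuous results only. Neither follows: the general rules exist, and PCS incidence is itself a count. What stands is that no laboratory shell applies the categorical rule and no layout shows morphology.
- Reticulocytes have by-visit minimum and maximum values. Their box plots follow a layout with 10th and 90th percentiles, outliers and the most frequent normal range. This shows roughly whether more than a tenth of subjects exceed that range, but not who moved from normal to high.

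A shift table also has limits. The protocol describes LDH and indirect bilirubin signs as increases, and a low/normal/high table misses a rise within the normal range. The planned change-from-baseline summaries serve better there.

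Finally, Protocol section 9 and SAP section 9 allow changes to be documented in the study report. A declared and justified omission would therefore be acceptable, but none is declared.

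**Conclusion.** The point holds as an undeclared departure from Protocol 9.6.2. The SAP plans no laboratory shift table (0 of 10 tables) and no by-visit count of categorical laboratory results. As a consequence, no laboratory table counts subjects with raised reticulocytes, abnormal RBC morphology, raised indirect bilirubin (except through total bilirubin of at least 2 mg/dL), or LDH above 1 but below 3 x ULN.

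This should be corrected before database lock. It does not mean that haemolysis goes unmonitored: marked changes are counted under Appendix B, and reported cases are counted as adverse events.

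The conclusion assumes that the tables listed in Appendix F and laid out in Appendix G are the complete planned set, and that the shells will be programmed as drawn. It makes no claim about how many subjects would be affected; the documents give no basis for one.

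**What to change.** In SAP 7.2 and Appendix F, restore the protocol's shift tables: low, normal or high at Baseline against each target week, at least for haemoglobin, RBC count, reticulocytes, LDH and total bilirubin. Add indirect bilirubin if the central laboratory supplies a normal range for it. The documents do not show that one exists for this calculated value; without it, rely on change from baseline. Add a by-visit count of subjects with abnormal RBC morphology, and a morphology column in Listing 16.2.8.2.1. A shift to the worst on-treatment value is optional, since the protocol asks only for target weeks. If the sponsor prefers to drop any of these tables, SAP section 9 should say so and give the reason.

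The cost is SAP wording and a modest amount of extra standard output. SAP 7.2 says central-laboratory flags are already in the data transfer. Appendix D already sets the worst-value rule within a visit window for haemoglobin, RBC count, reticulocytes, LDH and total bilirubin. A rule would have to be added for indirect bilirubin and RBC morphology.
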